4.5 Study Enrollment Procedures

Research staff will meet with area physicians via the CAPRICORN network and community members to inform them about the study. Flyers and posters will also be displayed in clinics, offices, and community centers participating in the study approximately three months prior to initiation of the study. Information about the study procedures and criteria will be available on a public, study-specific website (content pre-approved by the GU IRB).

Potential participants will be pre-screened over the phone or in-person using the Pre-screening Form (PS). If they meet basic entry criteria, the potential participant will be offered the opportunity for study participation and will be given a copy of the informed consent form and/or link to the website, and time to review before making the choice about participation. If the participant agrees, an enrollment and informed consent visit will be scheduled at a mutually agreed time and location. Information provided during the consent process include, the purpose of the study, procedures, withdrawal procedures, subject termination, risk/discomforts, benefits, costs, compensation, and alternatives to participation.

This study design is such that potential participants sign the informed consent about 45-60 days before starting any interventions. About 1-3 weeks after signing the informed consent, the participants have at least a 30-day wash out period where they refrain from consuming any probiotic products and antibiotics; after which, they will start the intervention period. Due to the time lag between enrollment and the start of the interventions, some participants decide to withdraw in the interim before starting any interventions. Since this is a study to understand the mechanisms of preventing antibiotic-associated diarrhea using probiotics, in order to accomplish the study aims, it is critical to have data collected from 60 participants who have been randomized and commenced the interventions. As such, we will enroll approximately 100 individuals to account for the withdrawal rates, so that study is completed with a final sample size of 60 participants.

5. STUDY INTERVENTIONS

5.1 Interventions, Administration, and Duration

The probiotic-supplemented yogurt is composed of the investigational agent, BB-12, and contains the yogurt starter culture YF-L702 (a mixed culture of *Streptococcus thermophilus* and *Lactobacillus delbrueckii* subsp. *bulgaricus*). The yogurt starter culture will be present and alive in the control yogurt. Starter culture alone is unlikely to impact AAD, as it does not survive the acidic stomach environment and is not recovered alive in the feces. Details about yogurt preparation, and enumeration and PCR verification of BB-12 have been previously published and reviewed by the United States Food and Drug Administration (FDA) Center for Biologics Evaluation and Research (CBER).

All participants will take the same amount of either the BB-12 or control yogurt, as determined by random assignment. Participants will each consume a four-ounce daily dose orally for 14 days while on amoxicillin-clavulanate for 7 days. Each four-ounce daily dose of the active yogurt will deliver no less than 10^{10} CFU of BB-12 per day.

Study interventions	BB-12 yogurt and amoxicillin-clavulanate, or Control yogurt and amoxicillin-clavulanate
Administration	Oral, to individual participants
Dosing schedule	4-ounces daily of BB-12 or control yogurt on days 1-14, and Amoxicillin-clavulanate 875/125 mg twice per day on days 1-7
Possible adverse events	See Section 7.3
Setting	Community
Intervention delivery	Research personnel will provide interventions Participants will self-administer
Use of appropriate supportive care, medications or treatments	Not applicable
Dose escalation procedures	Not applicable
Instructions for modifications	Not applicable
Package insert information	See package insert for amoxicillin-clavulanate

5.2 Handling of Investigational Product

5.2.1 Study Product Description

5.2.1.1 Acquisition

The investigational agent, *Bifidobacterium animalis* subsp. *lactis* (*B. lactis*) strain BB-12 (BB-12), will be supplied by manufacturer, Chr. Hansen, in Milwaukee, WI.

Chr. Hansen, Inc.
[name]
[name]

The investigational agent will be shipped directly from the manufacturer to The Pennsylvania State University where they will be added to the yogurts.

The Pennsylvania State University
Department of Food Science
[name]
[name]

5.2.1.2 Formulation, Packaging, and Labeling

The probiotic-supplemented yogurt is composed of the investigational agent, *Bifidobacterium animalis* subsp. *lactis* (*B. lactis*) strain BB-12 (BB-12), and also contains the yogurt starter culture, YF-L702 (a mixed culture of *Streptococcus thermophilus* and *Lactobacillus delbrueckii* subsp. *bulgaricus*).

The Chr. Hansen Culture Collection (CHHC) numbers of the exact strains used in the manufacture of the yogurt blend YF-L702 are *Streptococcus thermophilus* ST5389, *Streptococcus thermophilus* ST5086, *Streptococcus thermophilus* ST4460, *Lactobacillus delbrueckii* subsp. *bulgaricus* LB4351, and *Lactobacillus delbrueckii* subsp. *bulgaricus* LB2164.

Once manufactured, the probiotic-supplemented yogurt-drink will be packaged in pint-size plastic containers, which will yield 4 servings of the 4-ounce daily dosage. Four containers of the yogurt drink with their randomly assigned bin number will be provided to the participants after enrollment and the 4-week run-in period, prior to day 1, along with the plastic cups and markings that denote levels of 2, 4, 6, and 8 ounces. The daily dose is one serving of 4-ounces of yogurt each day. This will deliver no less than 10^{10} CFU per day of BB-12.

Each plastic container will bear the label "Caution: New Drug-Limited by Federal (or United States) law to investigational use" in addition to its manufactured date and time.

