5.2.1.3 Yogurt Drink Manufacture

Yogurt drink manufacture is broken into two major activities, 1) preparation of the yogurt and 2) blending with other ingredients to prepare the drink. To make the yogurt, a yogurt base is formulated to contain 9.0% milk solids non-fat (MSNF), 1.3% fat and 3.0% sugar using skim milk, cream, non-fat dry milk and sugar. The wet ingredients (skim milk and cream) are mixed together and then blended with previously weighed dry ingredients (sugar and non-fat dried milk). After blending the yogurt mix is pasteurized and homogenized (2000 psi first stage, 500 psi second stage) at 83°C for 29 sec. The pasteurized, homogenized mix is pumped to fermentation tank and given an additional heat treatment of 85°C for 30 min to denature whey proteins, then cooled to 42°C prior to inoculation with 0.02% of the yogurt starter culture (YFL-720). The inoculated mix is agitated for 15 minutes and then allowed to incubate quiescently until the pH reaches 4.6.

To prepare the yogurt drink the gel structure of the fermented yogurt is disrupted by agitation and blended with a mixture of pectin, 36 DE corn syrup solids, sugar and water. The pectin-containing mixture is prepared by heating water, sugar, 36DE corn syrup solids, and pectin to 80°C, holding for 1 hour. This mixture is then cooled to 40°C and added to the fermented white mass resulting in the unflavored yogurt drink base. To flavor the product, strawberry puree is then added to the yogurt drink. The composition of the yogurt drink is shown in Table 4 and the ingredients used in manufacture are listed in Table 5. At this point, a portion of the yogurt drink is homogenized (1500 psi first stage, 500 psi second stage) for a second time to create a drinkable consistency and packaged in plastic bottles. To prepare the yogurt drink containing BB12, an appropriate amount of (BB-12) is added to the yogurt drink, allowed to mix for 15 minutes and then homogenized and packaged as described above. The packaged yogurt is stored at 4°C.

Table 4. Composition of Strawberry Yogurt Drink

Component	Composition in Yogurt Drink
Fat	1.0%
Milk Solids Non-Fat	6.8%
Sucrose	6.1%
Corn Syrup Solids	6.4%
Pectin	0.4%
Strawberry Puree	3.0%

Table 5. Ingredients for Strawberry Yogurt Drink

Component	Supplier	Specifications
Milk ¹	Land-O-Lakes	PMO ²
Nonfat Dry Milk Solids ³	Various approved vendors	COA ⁴
Granulated Sugar ³	Various approved vendors	COA
Corn Syrup Solids ³ (42 DE)	Various approved vendors	COA

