6.5.3 Randomization

The group allocation ratio is 2:1, 40 BB-12 to 20 control volunteers. The randomization scheme will be generated by the study statistician, [name], using permuted blocks in random order: 4 blocks with the block size of 9 and 4 blocks with the block size of 6. It will be impossible for research personnel involved with participants to adjust randomization or discern what drinks participants were receiving, ensuring true allocation concealment. Participants who receive the control product will receive all identical interventions (i.e. stool collection, follow-up, etc.) that the BB-12 group receives.

Randomization will be completed after the participant consents to the study and completes the baseline assessment and run-in. The yogurt or antibiotic interventions may only be initiated after randomization.

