6.6 Blinding

Each participant will be randomly allocated in a 2:1 ratio to either BB-12-supplemented yogurt or an identical yogurt without the added BB-12 probiotic. Both contain the starter culture YF-L702 (a mixed culture of *Streptococcus thermophilus* and *Lactobacillus delbrueckii* subsp. *bulgaricus*). The yogurts are similar in taste and will have identical nutritional value, such as the same amount of calcium, protein, calories, etc. The yogurts are packed in identical packaging with six different bin numbers. The participants, PIs, research staff are all blinded to the treatment allocation.

The study statistician, [name], will generate three group-labels (e.g. A, B, C) where two groups are the same, e.g. A=C: BB-12 group, B: control group. [name] will be blinded to which two are the two treatment groups and which one is the control group. These groups will be considered as three arms before unblinding.

PSU will send yogurt in six bins with distinct numbers, two of which will be control yogurt and four will be the BB-12 yogurt. Only the researchers at Maryland will know which bin numbers correspond to 'group 1' and which correspond to 'group 2', but will not know which is the active or control. PSU and Maryland have no contact with participants and will not release this information to the study team until the analyses are completed and databases are locked.

All study personnel at Georgetown and [name] will remain blinded throughout the study until the databases are locked. In the unfortunate event that a participant experiences a serious adverse event or emergency that requires unmasking the treatment groups, [name], a member of the Department of Family Medicine who is not affiliated with the study, will discuss the assignment and follow-up with the participant and their treating physician. [name] has done this for our previous clinical trials.

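### The manufacture time printed on each bottle is undefined; if it is specific to a packaging run, it could let blinded site staff separate the two control bins from the four BB-12 bins

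*Combined protocol and SAP*

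**What the plan says.** - **Label.** Section 5.2.1.2 puts an investigational-use caution on each plastic container "in addition to its manufactured date and time".
- **Manufacture.** Section 5.2.1.3 starts from one flavoured base. "At this point, a portion of the yogurt drink is homogenized" a second time and bottled. For the other product, BB-12 is added to the drink, which is then "allowed to mix for 15 minutes and then homogenized and packaged as described above".
- **Bins.** Section 6.6 says that Penn State supplies six numbered bins, "two of which will be control yogurt and four will be the BB-12 yogurt". On appearance it says: "The yogurts are packed in identical packaging with six different bin numbers".
- **Who is blind.** Section 6.6 keeps participants, investigators and research staff blinded, with Georgetown personnel blinded until database lock. Section 6.5.3 goes further: "It will be impossible for research personnel involved with participants to adjust randomization or discern what drinks participants were receiving".
- **Who handles the bottles.** Study personnel bring the product to Washington (5.2.4.1), store it and arrange disposal by its expiry (5.2.4.2), and deliver it (5.2.4.3). At follow-up calls they check the participant's bin number against the randomization form (6.7.2).
- **What the site needs from the label.** Sections 5.2.4.2, 5.2.4.4 and 5.2.4.5 refer only to the date of manufacture. The time appears in Section 5.2.1.2 alone.

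**The concern.** Two products bottled in separate steps may carry different times. The split between arms is unequal and disclosed, so a visible grouping of the bins would also name the groups: the pair is control and the four are BB-12. With three bins per arm, the same grouping would leave open which group was which.

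The people who could see this are the people who must stay blind. Checking expiry makes them read the stamp, and the follow-up script ties each participant to a bin. The same team asks about adverse events and yogurt intake by telephone (5.4, 6.7.2). The investigator's view of relatedness, together with the participant's, decides whether some unexpected events are followed beyond Day 14 (7.7). The clinical investigator also takes part in withdrawal decisions after adverse events, and participants may be withdrawn as noncooperative (8). Knowledge of the arm could influence each of these without anyone opening the code.

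**Working it through.** The protocol gives no figure to reproduce here. The check is a count of how many assignments of bins to products remain possible under each meaning of the stamp.

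**Inputs.** Six bins, two control and four BB-12 (6.6); 40 BB-12 and 20 control participants (6.5.3). The bin ratio 4/2 = 2 matches the allocation ratio 40/20 = 2.

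**Without information from the label.** The number of possible control pairs is C(6,2) = 6!/(2! × 4!) = 15.

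**With the label, by what the stamp shows:**

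| Meaning of the printed stamp | Control pairs still possible |
|---|---|
| One common batch time and date on both products | 15 |
| Run-specific time, one run per product, visible gap between runs | 1 (the group of two bins) |
| Run-specific time, runs adjoin without a visible gap, order unknown | 2 (the two earliest or the two latest bins) |
| As above, with control known to be bottled first | 1 |
| Products made on different days, true dates printed | 1 (the date alone separates them) |

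Section 5.2.1.3 describes the drink without BB-12 first, but that is the order of the text and not a stated production schedule. If the four BB-12 bins were filled in more than one run, the pattern would no longer be a clean 2:4 split and the count could be larger.

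**Participants behind each bin.** With even use of the bins, which is an assumption, 40/4 = 10 and 20/2 = 10 participants are supplied from each.

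**Search for a safeguard.** No section masks the time, defines it as a batch time, or requires it to be the same across bins. Section 6.6 speaks of identical packaging but does not mention the stamp.

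**The case against.** The strongest reply is that the decisive fact is not in the protocol. The stamp could be the time of the shared base or a code for the production session; either would be the same on both products and reveal nothing. Section 5.2.1.3 lists processing steps, not a timetable, and does not say when a label is applied. The storage sections mention only a date, and Section 6.6 makes the bin number the only stated difference between packages. A stamp that differed by arm would conflict with that. This stands: the result is a risk left open, not a demonstrated unblinding.

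A reader might infer that one look in the refrigerator reveals the arm of all 60 participants. The documents do not support that. It would need run-specific stamps, one run per product, several bins seen and compared together, and a bin code that stays fixed over successive shipments. Section 6.6 does not say whether the code is fixed.

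A reader might also infer that the primary result is compromised. Acetate is measured by LC-MS/MS (3.1, 6.2.1.3), the decision to proceed to the R33 phase rests on the acetate effect size (9.1), and the secondary outcomes are 16S profiling and qPCR (3.2). These have little direct exposure. Table 9 lists stool frequency, Bristol chart and GSRS-IBS as diary outcomes, although Section 10.2.3 has research staff complete the GSRS-IBS form. A participant receives containers with one assigned bin number (5.2.1.2) and so cannot compare stamps across bins. An effect on who supplies stool samples is conceivable but speculative.

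The reply does not remove the gap. The same silence that prevents proof of a leak also means that the assurance in Section 6.5.3 has no support on this point.

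**Conclusion.** The point holds as a gap in the blinding procedure. The label carries a time whose meaning is undefined, the two products are packaged in separate steps, and the 2:4 split is disclosed. If the stamp is run-specific, or the manufacture dates differ, staff who see several bins could reduce 15 possible control pairs to 1 or 2. If a common batch time and date are printed, all 15 remain. The statement that staff cannot discern the product is therefore not secured by the labelling as written, but the documents do not show it to be false.

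This rests on two assumptions: that the labelling sentence, which follows a description of the probiotic drink, applies to control bottles too (supported by the identical packaging in 6.6 and by 5.2.4.2, which covers both products), and, for the counts of 1 or 2, that each product is bottled in one run. What is mainly at stake is the recording and judgement of adverse events, adherence and withdrawal by site staff.

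**What to change.** In Section 5.2.1.2, remove the time from the container label. Print one common expiry date, or a neutral delivery code, identical across all six bins of a delivery. Where the products are made on different days, set the expiry by the earliest-made product. Keep the true manufacture dates and times in the Penn State log. A common expiry date is preferable to a common manufacture date, which would be untrue for one product whenever the production days differ.

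Reconcile Section 5.2.1.2 with Sections 5.2.4.2, 5.2.4.4 and 5.2.4.5, which now rely on a printed date of manufacture, and with Section 6.6, which should state that everything printed on the bottle except the bin number is the same for both products. If the stamp is already a common batch mark, say so there.

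The cost is a label setting at the plant and a few sentences in the protocol. Traceability by time, and by exact manufacture date when the products are made on different days, will then need the plant log. In that second case, the later-made product also loses a little usable shelf life.

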5.2.1.3 Yogurt Drink Manufacture

Yogurt drink manufacture is broken into two major activities, 1) preparation of the yogurt and 2) blending with other ingredients to prepare the drink. To make the yogurt, a yogurt base is formulated to contain 9.0% milk solids non-fat (MSNF), 1.3% fat and 3.0% sugar using skim milk, cream, non-fat dry milk and sugar. The wet ingredients (skim milk and cream) are mixed together and then blended with previously weighed dry ingredients (sugar and non-fat dried milk). After blending the yogurt mix is pasteurized and homogenized (2000 psi first stage, 500 psi second stage) at 83°C for 29 sec. The pasteurized, homogenized mix is pumped to fermentation tank and given an additional heat treatment of 85°C for 30 min to denature whey proteins, then cooled to 42°C prior to inoculation with 0.02% of the yogurt starter culture (YFL-720). The inoculated mix is agitated for 15 minutes and then allowed to incubate quiescently until the pH reaches 4.6.

To prepare the yogurt drink the gel structure of the fermented yogurt is disrupted by agitation and blended with a mixture of pectin, 36 DE corn syrup solids, sugar and water. The pectin-containing mixture is prepared by heating water, sugar, 36DE corn syrup solids, and pectin to 80°C, holding for 1 hour. This mixture is then cooled to 40°C and added to the fermented white mass resulting in the unflavored yogurt drink base. To flavor the product, strawberry puree is then added to the yogurt drink. The composition of the yogurt drink is shown in Table 4 and the ingredients used in manufacture are listed in Table 5. At this point, a portion of the yogurt drink is homogenized (1500 psi first stage, 500 psi second stage) for a second time to create a drinkable consistency and packaged in plastic bottles. To prepare the yogurt drink containing BB12, an appropriate amount of (BB-12) is added to the yogurt drink, allowed to mix for 15 minutes and then homogenized and packaged as described above. The packaged yogurt is stored at 4°C.

Table 4. Composition of Strawberry Yogurt Drink

Component	Composition in Yogurt Drink
Fat	1.0%
Milk Solids Non-Fat	6.8%
Sucrose	6.1%
Corn Syrup Solids	6.4%
Pectin	0.4%
Strawberry Puree	3.0%

Table 5. Ingredients for Strawberry Yogurt Drink

Component	Supplier	Specifications
Milk ¹	Land-O-Lakes	PMO ²
Nonfat Dry Milk Solids ³	Various approved vendors	COA ⁴
Granulated Sugar ³	Various approved vendors	COA
Corn Syrup Solids ³ (42 DE)	Various approved vendors	COA
Pectin ADM 783	DuPont, New Century, KS	COA
Strawberry Puree #242529384	Sensient Flavors, Amboy, IL	COA
YF-L702 (starter culture)	Chr. Hansen, Milwaukee, WI	COA
BB-12 (probiotic)	Chr. Hansen, Milwaukee, WI	COA

¹ Milk is received on an as needed basis and is purchased from Land-O-Lakes.

² Milk will be produced under and meet the requirements of the Pasteurized Milk Ordinance (PMO).

³ The supplier for nonfat dry milk, sucrose and corn syrup solids may change based on availability and price of ingredient.

⁴ All ingredients will be food-grade and a will require a Certificate of Analysis (COA) from the supplier.

5.2.1.4 Enumeration of BB-12 from the Yogurt

The viable count of BB-12 in the product is measured the day of manufacture (Day 0) and weekly until Day 30 of shelf-life. The yogurt drink is diluted in sterile peptone water blanks (3M, St. Paul, MN) and then appropriate dilutions of the product are cultured by pour plating on an MRS-based selective bifidobacteria medium.(103) Modified MRS agar is made by adding 4.5 grams Agar (Difco, BD, Sparks, MD) to 300 ml MRS broth (Difco, BD, Sparks, MD). After autoclaving, the agar is used immediately after addition of three selective components, 1.5mL of 0.01% Dicloxacillin (Sigma-Aldrich, St. Louis, MO); 3.0 mL of 10% Lithium Chloride (Sigma-Aldrich, St. Louis, MO); and 1.5 mL of 10% Cysteine Hydrochloride (Sigma-Aldrich, St. Louis, MO). Plates are anaerobically incubated (VWR, West Chester, PA) at 37°C and counted after 72 hours. The final yogurt drink also is evaluated for the presence of coliforms using high sensitivity PetrifilmTM Coliform Count Plates (3M™, Burlington, North Carolina) and Petrifilm™ aerobic plate counts according to the 17th edition of Standard Methods for the Examination of Dairy Products, #7.072 and #6.040, respectively.

5.2.1.5 PCR Verification of BB-12 Level in Finished Yogurt

To further verify the selectivity of the BB-12 agar, colonies of varying morphology are selected for identification using *B. lactis* specific PCR primers according to the method of Ventura et al.(104) Cells are lysed according to the microwave method of Bollet et al. as modified by Kullen et al.(105, 106) The sequence of the forward primer, Bflact2, is 5'-GTGGAGACACGGTTCCC-3' and the reverse primer, Bflact5, is 5'-CACACCACACAATCCAATAC-3'. Amplicons from PCR are electrophoresed through a 2% agarose gel at 110 volts for 2 hours, stained with ethidium bromide (Promega, Madison, WI), destained with distilled water and visualized using an Alpha-Imager (Alpha Innotech, San Leandro, CA). The presence of amplicons of the appropriate size is taken as evidence the colonies are indeed *B. lactis*.

